Dry anal and cervicovaginal specimens will be processed and tested using the Atila Ampfire HPV genotyping. Upon arrival, the oral rinse specimen containers will be stored at 4°C refrigerators for processing the next working lab day. Dry brushes and associated labels will be stored in a box in the freezer at -20°C for processing the next working lab day. After testing, residual specimens will be aliquoted and stored frozen at -20°C for further testing.

[figure not shown]
HPV genotyping will be conducted within 2 months of collection to allow ample time to schedule the 6-12 month follow up visit for women who test HPV positive for any HPV type at any tissue site.

VI.F.2. Follow-Up Visit of the HPV-Positive Cohort

Participants who test positive for any of the 17 HPV types on their cervicovaginal, oral, and/or anal specimen collected at baseline will be scheduled for a 6-12 month follow-up visit with a window of 5-15 months after their baseline visit; participants who test negative on all three specimens will exit the study. Objectives of the follow-up visit are to 1) measure 6-12 month HPV persistence, an accepted primary endpoint in prophylactic HPV vaccine trials (89), and 2) ensure the safety of the participants. As outlined in **Figure 3**, at the follow-up visit, the participant's eligibility status will be confirmed. Participants will provide a urine sample for pregnancy testing to confirm they are not pregnant. Counseling will be provided pre and post testing as needed. Participants unknown to be living with HIV will have a rapid HIV test with pre- and post-HIV-testing counseling following the National Rapid HIV Diagnostic Testing Protocol. Any participant who tests positive will be referred to the health center's HIV clinic for

HIV management following the Ministry of Health's HIV management guidelines. Only specimens from those anatomic sites that were HPV positive at baseline will be collected utilizing the same protocol as at enrollment. A study staff will transport the oral saline rinse and dry swabs to the study lab to be stored until study testing for 17 HPV genotypes; the follow-up cervicovaginal and anal specimens will be tested within one month to ensure timely follow-up of high-risk individuals who need diagnostic services (colposcopy and/or anoscopy).

Figure 3. Activities at follow-up visit

VI.G. Study Test Results and Clinical Management

VI.G.1. Management of Persistent Cervicovaginal HPV

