All histopathology slides will be scanned at the study lab and reviewed by two local pathologists and the Einstein study pathologist (105). If the diagnoses are concordant, no further review of the case will be performed. If the diagnosis is discordant and at least one pathologist diagnoses CIN2+, the biopsy slide will be subjected to a joint review and consensus diagnosis. For Negative/cervical intraepithelial neoplasia grade 1 pairs of diagnoses, which does not influence our analyses or the care of the participants, there will be no joint review.

VII. STATISTICAL SECTION

VII.A. Specific Aim 1

To measure population effectiveness of prophylactic HPV vaccine in reducing cervicovaginal, anal, and/or oral prevalent and persistent infections by HPV6/11/16/18.

VII.A.1. Analyses.

We will calculate the point prevalence and the prevalence of persisting infection by individual HPV-type specific infections, with binomial 95% confidence intervals (95% CI), for each anatomic and for the woman (all anatomic sites) for Gardasil®-vaccinated WLWH, Gardasil®-vaccinated HIV[-] women, unvaccinated WLWH and unvaccinated HIV[-] women. We likewise will calculate the point prevalence and the prevalence of persisting infection with 95%CI for all

HPV types in aggregate and in sub-groups of HPV types according to the protection afforded by Gardasil®: Gardasil®-targeted types (HPV6, 11, 16, and 18), Gardasil®-untargeted types for which there might be cross-protection (HPV31, 33, and 45) (40, 106, 107), and Gardasil®-untargeted HPV types for which there is little or no evidence of cross-protection (HPV35, 39, 51, 52, 53, 56, 58, 59, 66, and 68). Results will be stratified by age and number of doses (3 vs. 2) as well as other factors possibly associated with HPV prevalence. Differences in the prevalence of these HPV type sub-groups (targeted, possible cross-protection, and untargeted) between the four study groups of women will be tested using Fisher's exact or Pearson chi-square test. Differences in the prevalence of these HPV type subgroups by age, number of doses (3 vs. 2), and other factors within the group, will be tested for statistical significance ($p<0.05$) using a Fisher's exact or Pearson chi-square test.

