Similarly, exploratory analyses will compare the effectiveness of HPV vaccination for cross-protection types and endpoints of cumulative detection of Gardasil®-targeted HPV types-associated CIN2+ and/or anal intraepithelial neoplasia grade 2 or more severe (AIN2+) (vs. untargeted HPV type-associated CIN2+ and/or AIN2+) between study groups.

For participants in the existing IeDEA database we will extract HIV specific variables. For those who we cannot match to the IeDEA database, will extract HIV specific variables from medical records.

In another exploratory analysis, among WLWH, the presumed route of HIV acquisition (either maternal to child or behavioral) will be compared with HPV positivity and, among HPV-positive women, HPV viral load.

VII.A.2. Sample Size/Power for Gardasil®-vaccinated vs. unvaccinated WLWH.

For this analysis, we will make the following assumptions: 1) at least 30% prevalence of HPV infection (of any anatomic site) at baseline, 25% of which will be Gardasil®-target HPV types and 55% will be untargeted HPV types, 2) a 10% loss to follow-up (LTFU) in at follow up visit, and 3) at least 70% of HPV infections persist for 6-12 months. We justify an HPV prevalence of at least 30% based on 30% prevalence of high-risk HPV infection of the cervix in 30-year-old WLWH from our previous U54 study (109). We expect that the HPV prevalence may be higher since the prevalence of HPV, like that of other sexually transmitted infections, tends to peak about 5 years after the median age of sexual initiation in a population. However, we conservatively used 30% to ensure adequate statistical power. We justify our assumption of a maximum of 10% follow-up, given our experience working in Rwanda over the last ~20 years. We justify 70% of prevalent HPV infections persisting for 6-12 months, given that 36-50% of prevalent HPV infections persist 6-months in HIV[-] women (109, 110) and WLWH have an impaired immunity to HPV (8, 9).

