Using the variance of GMT for HPV antibodies from Einstein et al. (111, 112), a sample size of at least 274 will provide 80% power ($p=0.05$) to detect a 30% difference in GMT between HPV-vaccinated WLWH and HIV[-] women for a given number of doses. If there is no appreciable difference in the titers between those who got 3 or two doses, we can combine those groups with different doses. In that case, with a sample size of at least 548, there will be 80% power ($p=0.05$) to detect a 22% difference between HPV-vaccinated WLWH and HIV[-] women.

VII.C. Exploratory Aim: A Study of 6-12 Month Type-Specific HPV Persistence

Given the size of the cohort of WLWH (n=1,514 at baseline), the planned follow-up of the HPV-positive WLWH, and the laboratory assay capacities that are available and will be

developed at the study lab, we have unique opportunity to look at determinants of early, short-term HPV genotype-specific persistence/clearance in young women. Studies of HPV persistence in WLWH, especially in SSA, are limited in number and size (113-120). There is a growing body of evidence that an altered CVM (cervicovaginal dysbiosis) is associated with persistent HPV infection (86) but there are no published data on its role in HPV persistence in WLWH. There is evidence of greater cervicovaginal microbiotic diversity in WLWH compared to HIV[-] women (121) and a complex, possible inter-dependence of CVM and HPV natural history (122). Given the importance of short-term HPV persistence as a biomarker of cervical-cancer risk (123) as well as an endpoint for prophylactic HPV vaccine trials, this is a unique opportunity to understand its determinants.

Paired baseline and follow up specimens from participants whose baseline cervicovaginal specimen tests HPV positive will have their cervicovaginal microbiome characterized. We will examine factors such as baseline and history (if available) of HIV disease status (HIV viral load and CD4), the presence of the HPV genotype at other anatomic sites, CVM composition, and other risk factors (e.g., sexual behaviors) on whether HPV infection persists vs. clears.

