We are using 6-12 month persistence as a proxy for cancer risk but ideally, we want to measure the impact of Gardasil® on high-grade cervical and anal abnormalities as a more proximal surrogate for cancer risk. The population will be still too young to have large numbers of these endpoints although we will look at these endpoints in secondary analyses. The longer-term effectiveness of Gardasil® through years of peak HPV exposure cannot be assessed in the 5-year time period of a single grant.

Our hope is to conduct follow-up studies of this newly established cohort of WLWH to assess the durability of immunogenicity and protection, including protection against high-grade cervical and anal abnormalities, offered by HPV4 for WLWH, as well as continuing to study the natural history of HPV in WLWH living in SSA. Eventually, as noted above (**Section VIII.**), we will be

[figure not shown]
well-positioned to examine the impact of HPV vaccination on cancer incidence in WLWH by linkage of electronic databases that we have helped/will help create.

XII. DISSEMINATION OF RESEARCH RESULTS

[figure not shown]
We plan to publish a series of 10 or more scientific reports in peer-review scientific journals. As building research capacity in Rwanda is a major goal of this U54 grant, all members of the research team will be asked and supported to lead at least one analysis and one manuscript preparation, based on interests and expertise. A publication grid is in development to assign analytic and publication responsibilities equally and collaboratively among both Rwandan and U.S. investigators.

XIII. TIMELINE

Pending approvals and situations in the field with the COVID-19 pandemic, we anticipate starting enrollment in September 2021. Enrollment will take approximately 14-16 months with completion of follow-up visits 6-12 months after that. All colposcopy and treatment visits should be completed by mid-2023.

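### Visits from 5 to 15 months all count as 6-12 month persistence and no analysis uses the actual interval, so the VII.C model and, less so, the crude persistence comparisons could partly reflect visit timing

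*Combined protocol and SAP*

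**What the plan says.** Section VI.F.2 gives the follow-up visit two ranges. It is called a 6-12 month visit and is meant to "measure 6-12 month HPV persistence, an accepted primary endpoint in prophylactic HPV vaccine trials", but it is accepted "with a window of 5-15 months after their baseline visit". Persistence is a yes/no result at that single visit.

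The persistence analyses are these:

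- Section VII.A.1 will calculate "the prevalence of persisting infection by individual HPV-type specific infections" with binomial confidence intervals for the four study groups. Differences between groups, and by number of doses, are tested with Fisher's exact or chi-square tests.
- Section VII.A.1 also defines the main effectiveness measure, a logistic odds ratio of targeted against untargeted types compared between groups. Further adjustment is optional; age, doses and sexual behaviors are named as examples.
- Section VII.C examines HIV markers, the same genotype at other sites, the microbiome and other risk factors "on whether HPV infection persists vs. clears". It uses a logistic GEE model. Factors enter after a univariate screen at p<0.1, followed by forward and backward selection.

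None of these names the time between visits, and no analysis is restricted to visits at 6-12 months.

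On calendar time, Section XIII expects enrolment from September 2021 for about 14-16 months, with follow-up visits finished 6-12 months later. It then adds: "All colposcopy and treatment visits should be completed by mid-2023".

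**The concern.** An infection has more time to clear by 15 months than by 5. If two groups return at different times, a yes/no persistence result will differ between them even when clearance is identical. Nothing planned would reveal or remove that difference.

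The VII.C model is the most exposed. It is conditional on being infected at baseline and has no internal comparator, and the interval is not among its named factors. Any factor related to return time could pick up a timing effect. One candidate is built into data collection: Appendix IV counts partners since the last visit, a count that grows with the interval. The plan does not say whether those answers, rather than the enrolment ones, are the sexual behaviors to be modelled.

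The crude comparisons in VII.A.1 are exposed in the same way, but diluted if the denominator is all women rather than infected women.

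**Working it through.** **No figure in the plan to reproduce.** The plan gives no calculation on visit timing. Its power statement for persistence is a separate matter and is not used here.

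**Inputs.** From Section VII.A.2: "at least 30% prevalence of HPV infection (of any anatomic site) at baseline", 10% loss to follow-up, "at least 70% of HPV infections persist for 6-12 months" (WLWH), and "36-50% of prevalent HPV infections persist 6-months in HIV[-] women". From Section VI.F.2: the 5-15 month window. Assumptions added here: a constant clearance rate, the 70% placed at 9 months (the middle of 6-12), and all mean visit gaps.

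**Step 1. Persistence by visit month.** Rate = -ln(0.70)/9 = 0.0396 per month; S(t) = exp(-0.0396t).

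| Month | 5 | 6 | 7 | 8 | 9 | 10 | 12 | 15 |
|---|---|---|---|---|---|---|---|---|
| S(t) | 0.820 | 0.788 | 0.758 | 0.728 | 0.700 | 0.673 | 0.622 | 0.552 |

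**Step 2. Spurious odds ratio with identical clearance.**

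- Among infected women: OR = [S(a)/(1-S(a))] / [S(b)/(1-S(b))]. For 8 versus 10 months, 2.68/2.06 = 1.30. For 6 versus 12 months, 3.73/1.64 = 2.27.
- Among all enrolled women: the followed-up positive fraction is 0.30 × 0.90 = 0.27, so the prevalence of persisting infection is 0.27 × S(t). For 8 versus 10 months, 0.197 versus 0.182, OR about 1.10. For 6 versus 12 months, 0.213 versus 0.168, OR about 1.34.

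**Step 3. Sensitivity to the anchor (infected women).**

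| Anchor | 8 vs 10 months | 6 vs 12 months |
|---|---|---|
| 70% at 6 months | 1.33 | 2.43 |
| 70% at 9 months | 1.30 | 2.27 |
| 70% at 12 months | 1.29 | 2.20 |
| 50% at 6 months (HIV[-]) | 1.43 | 3.00 |
| 36% at 6 months (HIV[-]) | 1.55 | 3.78 |

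**Step 4. False rejection.** With 757 × 0.30 × 0.90 = 204 infected women followed per group, 70% at 9 months and no true difference, a two-sided 5% test of two proportions rejects with probability 9% for mean visits at 8.5 versus 9.5 months, 23% for 8 versus 10, and 96% for 6 versus 12.

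**Step 5. The main relative odds ratio.** Both type classes are measured at the same visits. With no vaccine effect, and 9-month persistence sT (targeted) and sU (untargeted), timing alone multiplies the ratio by (sT/sU)^((a-b)/9). If sT = sU this is 1.00 for any gap. At 75% versus 65% it is 0.97 (8 versus 10 months) or 0.91 (6 versus 12). At 80% versus 60% it is 0.94 or 0.83.

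**Step 6. Can the interval differ by group?** Table 3 in Section VI.C places two-dose women in birth years 2003-2005, and the minimum age is 18. Those born in 2004 can enrol only from 2022 and those born in 2005 only from 2023. Under Section XIII, enrolment ends between about November 2022 and January 2023. That leaves the last women roughly 5-8 months to mid-2023. Follow-up visits 6-12 months after enrolment would run from about May 2023 to January 2024. At the long end, the two Section XIII statements do not fit together.

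**The case against.** The strongest reply is that the analysis that matters most is hardly touched. The plan knows the groups are not comparable and answers with a relative odds ratio, and it is the measure that Section VII.A.2 powers. Step 5 confirms that timing cancels there unless the type classes clear at different rates, and that the residual is modest. This stands.

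A reader might go further and infer that two-dose or late-enrolled women will look more persistent. The documents do not support that. They contain no interval data. Each visit is scheduled from the woman's own baseline, with genotyping within two months so that it can be arranged. Women born in 2003 are also two-dose and can turn 18 during 2021. Section XIII itself allows follow-up 6-12 months beyond enrolment, and its dates are made conditional on approvals and the pandemic.

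A reader might equally infer a spurious HIV or microbiome association. Table 3 sets the same birth-year and dose quotas for WLWH and HIV[-] women, so a calendar effect would tend to fall on both alike. Nothing in the plan suggests that microbiome composition tracks return time.

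On size, the odds ratios of 1.30 to 2.27 apply only among infected women. VII.A.1 reports prevalence by study group, most naturally read as a share of all women, where the smaller figures apply. The 6 versus 12 month contrast puts group means at opposite ends of the scheduled range.

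Finally, VII.C is exploratory and its factor list is open, so the interval is not excluded. True, but it is not planned either. If added as an ordinary candidate, it could be dropped by the p<0.1 screen or the stepwise selection.

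**Conclusion.** The concern holds as a potential timing bias together with a mismatch between the endpoint's name and its accepted window. It is strongest in the exploratory VII.C model and smaller in the crude VII.A.1 persistence comparisons. The main relative odds ratio is largely protected, and this point is not evidence that it is biased.

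With identical clearance, the spurious odds ratio is 1.30 to 2.27 among infected women, or about 1.10 to 1.34 among all enrolled women, for mean gaps of 8 versus 10 to 6 versus 12 months. These figures rest on constant clearance, 70% persistence at 9 months, and hypothetical gaps. They show what timing could do; the documents do not show that a gap will arise or in which direction. The correction is worth making because it is nearly free and uses dates already needed to apply the window.

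**What to change.** 1. Tabulate months from baseline to follow-up by study group and dose group.
2. In Section VII.C, force the interval (in months) into the GEE model, exempt from the p<0.1 screen and the stepwise selection.
3. Include it in any adjusted between-group model of absolute persistence. The targeted/untargeted relative odds ratio does not need it as a matter of course.
4. Describe the main endpoint as persistence at a 5-15 month visit, and add a sensitivity analysis restricted to visits at 6-12 months.
5. Reconcile the two Section XIII statements on when follow-up and when colposcopy and treatment visits finish.

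The cost is analysis wording, one degree of freedom, and a smaller sample in the sensitivity analysis. No visit, specimen or management rule changes.

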Cervical cancer is the 4th most common cancer and cause of cancer-related death in women globally; in many lower-resource settings, especially sub-Saharan Africa (SSA), it is the most common. Virtually all cervical cancer and precancer are caused by 12-15 high-risk human papillomavirus (HPV) types. HPV16 causes approximately 55-60% and HPV18 causes approximately 10-15% of cervical cancer while the remaining 12 HPV types cause the remaining 25-30% of cervical cancer. High-risk HPV, predominately HPV16, also causes most anal, vulvar, vaginal, and penile cancers and a significant proportion of oropharyngeal cancers. Prophylactic HPV vaccines have been developed and have been shown to be nearly 100% protective against incident HPV infection and related abnormalities in the general population. However, the evidence for the effectiveness of prophylactic HPV vaccines in women living with human immunodeficiency virus (HIV) (WLWH) is less clear. HIV infection increases the risk of cervical cancer due to an impaired immune response to HPV.

Rwanda is a high-burden cervical cancer country where the prevalence of HIV is 3.7% among adult women, with higher HIV prevalence among young women (1). In 2011, Rwanda implemented a national HPV vaccination program with Gardasil®, which protects against HPV16 and HPV18, the two HPV types that cause ~70% of cervical cancer, and HPV6 and HPV11, the two types that cause ~90% of anogenital warts (HPV6/11/16/18). Their program has achieved >90% coverage of the target population, primarily girls aged 12 years, annually. The implementation of a highly successful HPV vaccination program and the high prevalence of HIV, in addition to the research and medical capacity that Albert Einstein College of Medicine (Einstein) has helped to build at the Rwanda Military Hospital (RMH), Research for Development (RD Rwanda) and University of Rwanda (UR), makes Rwanda the ideal locale to study the long-term effects of HPV vaccination in WLWH.

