A summary of the management of HPV-positive results is shown in **Figure 4**. To ensure the safety of participants, those who at the follow up visit, have a type-specific persistent HPV infection for one or more of the 15 hrHPV types (HPV16/18/31/33/35/39/45/51/52/53/56/58/59/66/68), regardless of HIV status, will be referred to colposcopy. Colposcopy and treatment will be performed at RMH by a trained study physician or gynecologist on staff at the hospital.

Digital images of the cervix will be taken using a study-provided contemporary digital camera (e.g., Samsung A21S or similar cellular phone camera). The participant's images will be shown to her if she so desires. All images from a participant will be identified using a study ID. Images will not be analyzed at the clinic visit but be stored in the study secure NIH server immediately or, if not possible at the time, images will be uploaded when secure access to the study server becomes available. Images will be used for later analyses with automated visual evaluation algorithms being developed at the NCI for management of HPV-positive women (90).

Biopsies will be taken of all acetowhite, visible cervical abnormalities consistent with the American Society for Colposcopy and Cervical Pathology (ASCCP) management guidelines (91). The colposcopy impression and location of biopsies will be recorded for clinical management files and saved in the participant record for study purposes.

[figure not shown]

Figure 4. Follow-up and Clinical Management of Baseline HPV-Positive Results

After undergoing colposcopy and biopsies, WLWH with persistent HPV16- or HPV18 infection will receive ablative treatment unless ineligible for ablative treatment per WHO Guidelines (92); those ineligible for ablation will receive treatment by LEEP. Biopsies will be read by two local pathologists and [name] (Einstein). All participants diagnosed with CIN3+ will undergo treatment. In accordance with ASCCP guidelines, those diagnosed with CIN2 will not undergo immediate treatment due to the low risk of ICC following a CIN2 diagnosis, especially in young women, and the possible increased risk in negative reproductive outcomes such as pre-term delivery following treatment (10). They will be advised to seek clinical follow-up in a year.

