After processing and reading according to local practices, formalin-fixed paraffin-embedded (FFPE) tissue specimens from biopsies and excisional treatment with results of CIN2+ will be sent to the study lab for HPV typing for study purposes (**Section VI.I.1.**).

To summarize, within the context of the research protocol, participants at risk of precancer will be provided with colposcopy as well as treatment and follow-up. Participants with a diagnosis that requires treatment beyond ablation or excision (i.e., invasive cervical cancer), will be referred and guided to appropriate local care.

VI.G.2. Management of Persistent Anal HPV

WLWH with persistent HPV16 or HPV18 infection will undergo anoscopy; HIV[-] participants with persistent HPV16- or HPV18 infection will not undergo anoscopy due to their still low absolute risk of anal cancer (10) and the morbidity of treating anal abnormalities. Anoscopy and treatment will be performed at RMH by a study physician on staff at the hospital with training for this protocol.

A biopsy will be taken from acetowhite lesions. The anoscopy impression and location of biopsies will be recorded for clinical management files and saved in the participant record for study purposes. After processing and reading according to local practices, formalin fixed, paraffin embedded (FFPE) tissue specimens from biopsies and excisional treatment with results of anal intraepithelial neoplasia (AIN) grade 2 (AIN2) or more severe diagnoses (AIN2+) will be sent to the study lab for HPV typing analysis (**Section VI.I.1.**).

Those with a biopsy diagnosis of AIN grade 3 (AIN3) or anal cancer will be treated or referred for anal cancer management, respectively. Those diagnosed with AIN2 will not undergo immediate treatment due to the low risk of anal cancer following a AIN2 diagnosis and the aforementioned morbidity associated with treatment. Those with untreated AIN2 or persistent anal hrHPV by non-HPV16/18 types will be advised to seek clinical follow-up in a year.

Similar to colposcopy, within the context of the research protocol, participants at high risk of anal precancer will be provided with anoscopy as well as treatment and follow-up. Participants with a diagnosis that requires treatment beyond routine care (i.e., invasive anal cancer) will be referred and guided to appropriate local care.

VI.G.3. Management of Persistent Oral HPV

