There are no management guidelines or evidence-based intervention for type-specific persistent HPV. Therefore, participants will not receive any clinical intervention for type-specific persistent oral HPV.

VI.G.4. Study Exit

Other participants, including WLWH and/or those with persistent low-risk HPV6- or HPV11 infection, will exit the study.

VI.H. Biospecimen Processing, Storage, and Shipment

The study lab will process, store and test for HPV in oral specimens in saline solution, dry samples, blood samples and FFPE tissue specimens. All specimens will be tested for individual 17 HPV types using the AmpFire HPV genotyping test.

In preparation for testing, oral specimens will be aliquoted, the dry sample will be rinsed into a vial with lysis buffer and FFPE tissue specimens will be suspended in lysis buffer. Specimens will be processed according to manufacturer's instructions. All residual lysed specimens will be stored at the study lab at -80°C for later testing. Select samples will be sent to study collaborators' laboratory for microbiome testing. Additional microbiome testing will be conducted at the study lab.

Whole blood specimens will be processed to obtain aliquots of plasma. Following the protocol established by the Frederick National Laboratory of Cancer Research (FNLCR) HPV Serology Laboratory, select plasma specimens will be sent to FNLCR for testing and others will be tested at the study lab (**Section V.I.2**). After ELISA testing, residual plasma will also be stored at the study lab for later testing.

A biospecimen bank containing residual material from samples collected will be established at the study lab for subsequent methodologic and etiologic research.

VI.I. Laboratory Testing

VI.I.1. AmpFire HPV Testing

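### As worded, the one-year anal advice in VI.G.2 leaves out HIV[-] women whose only persistent anal high-risk type is HPV16 or HPV18, while covering the 13 other high-risk types

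*Combined protocol and SAP*

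**What the plan says.** Section VI.G.2 deals with persistent anal infection. WLWH with persistent HPV16 or HPV18 have anoscopy. For the others it says "HIV[-] participants with persistent HPV16- or HPV18 infection will not undergo anoscopy due to their still low absolute risk of anal cancer", and it adds the morbidity of treating anal abnormalities as a second reason. After describing biopsy and the handling of AIN3 and cancer, it says "Those with untreated AIN2 or persistent anal hrHPV by non-HPV16/18 types will be advised to seek clinical follow-up in a year". The closing paragraph of the section says that "participants at high risk of anal precancer will be provided with anoscopy as well as treatment and follow-up".

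Section VI.G.4 then disposes of everyone else: "Other participants, including WLWH and/or those with persistent low-risk HPV6- or HPV11 infection, will exit the study".

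Three other places bear on the point:

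- Section VI.G.1 gives the 15 high-risk types and refers women with persistent cervicovaginal infection by any of them onward; these women, "regardless of HIV status, will be referred to colposcopy".
- The Executive Summary says: "High-risk HPV, predominately HPV16, also causes most anal, vulvar, vaginal, and penile cancers".
- Section VI.A offers anoscopy for persistent anal HPV16/18 to participants in general. Sections VI.G.2 and X.A.2 restrict it to WLWH.

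**The concern.** The advice sentence sorts women by HPV type and carries no HIV limit. Its omission of HPV16/18 is logical only if women with those types are looked after in another way. WLWH are, by anoscopy. HIV[-] women are not, because the same section takes anoscopy away from them and puts nothing in its place.

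Followed to the letter, the text gives an HIV[-] woman advice for the types the protocol ranks lower and none for the two it ranks higher. The stated reasons for withholding anoscopy, low absolute risk and treatment morbidity, do not explain this, since advice to seek care carries no procedural morbidity.

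One of the two stated aims of the follow-up visit in VI.F.2 is to "ensure the safety of the participants", and staff need one clear disposition for each result. The decision not to perform anoscopy in HIV[-] women is not in question here.

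**Working it through.** The point is textual, and the only arithmetic is a count.

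**Count of types.** VI.G.1 states 15 high-risk types. Its list is 16, 18, 31, 33, 35, 39, 45, 51, 52, 53, 56, 58, 59, 66 and 68, which is 15, so the stated figure is reproduced. Taking out HPV16 and HPV18 leaves 15 − 2 = 13 types that trigger the one-year advice.

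**Disposition of a persistent anal infection, on the literal text:**

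| Only persistent anal high-risk type | WLWH | HIV[-] women |
|---|---|---|
| HPV16 or HPV18 | Anoscopy (VI.G.2) | No anoscopy (VI.G.2), no advice; exit for the anal result (VI.G.4) |
| Any of the other 13 | Advice (VI.G.2) | Advice (VI.G.2) |

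**Whom the advice sentence covers.** It has two limbs. Untreated AIN2 can arise only after an anal biopsy, hence only in WLWH. Persistent infection by a non-16/18 type leads to anoscopy for nobody, so this limb must reach women who were never biopsied. The sentence therefore cannot be confined to the biopsied group, and nothing in it confines it to WLWH.

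**Risk order within the document.** The Executive Summary names HPV16 as the predominant type in a group of cancers that includes anal cancer, and VI.G.2 makes HPV16 and HPV18 the trigger for anoscopy. For HPV18 the ranking rests on that trigger alone. On both counts the lower right-hand cell of the table should not receive more than the upper right-hand one.

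**Who is not caught by the gap.** An HIV[-] woman with HPV16/18 and another persistent anal high-risk type is advised because of the other type. One with persistent cervicovaginal high-risk infection is still referred to colposcopy. The gap concerns anal advice only.

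**Section VI.A.** Its anoscopy offer has no HIV limit, while VI.G.2 and X.A.2 both have one. Two specific sections agree, and the overview is the outlier.

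**The case against.** The strongest reply is that the sentence was meant for WLWH only. VI.G.2 deals with HIV[-] women at the outset, and the rest follows the anoscopy pathway, which only WLWH enter. If HPV16/18 does not justify work-up in HIV[-] women, less risky types justify it even less. On that reading there is no inverse order of risk. The protocol does state HIV scope in some places, but it also drops the WLWH limit where it must mean it, as in VI.A and in the closing paragraph of VI.G.2. A missing qualifier is therefore weak evidence that all participants were intended. This stands: the WLWH-only intent is plausible, though unwritten.

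Second, VI.G.1 says: "A summary of the management of HPV-positive results is shown in" Figure 4. That figure could not be read, nor could the consent form, and either may already give the disposition. This also stands, and it limits the point to the readable text.

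Third, VI.A is a design overview and VI.G.2 is the operative section, so anyone managing a participant would find the right rule. That is fair, and it makes the VI.A mismatch an editorial matter.

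A reader might infer that the study will in practice manage HIV[-] women in inverse order of risk. The documents do not support that. It would require the literal reading to be the intended one, and Figure 4 and the working procedures to add nothing. Nor do they support the inference that HIV[-] women should have anoscopy, since the protocol gives reasons against it.

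**Conclusion.** The point holds as a defect of wording, and it is minor. On the readable text, an HIV[-] woman is advised for 13 of 15 persistent anal high-risk types, and the two left out are HPV16 and HPV18. The conclusion assumes that the sentence applies as written and that the unreadable figure and consent form do not already cover the case.

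The 13 of 15 is a count of types and says nothing about how many women are involved. The documents give neither the prevalence of anal HPV16/18 nor its persistence in HIV[-] women, so no number can be given. What is at stake is a message to seek care outside the study. No endpoint, test, sample size or analysis changes.

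**What to change.** In VI.G.2, add a third group to the one-year advice sentence, after untreated AIN2 and persistent non-16/18 anal infection: HIV[-] participants with persistent anal HPV16 or HPV18. This gives HIV[-] women the same advice for all 15 types and leaves the rule for WLWH unchanged.

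If the sponsor intended the sentence for WLWH only, the minimum is to say so and to state that HIV[-] women exit for their anal result whatever the type. That clarifies the text but does not improve what participants receive.

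In VI.A, insert a limit to WLWH before the anoscopy offer, to match VI.G.2 and X.A.2. Then check that Figure 4, the consent form and the participant result text agree.

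The cost is two short wording changes and matching result text, with no new visit, test or procedure. The downside is that a few low-risk HIV[-] women receive an extra advice message, the same one the section as worded already gives for the other types.
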